6.2.2.6.1 Anaphylaxis and Serious Allergic Reactions

Anaphylaxis will be defined according to the National Institute of Allergy and Infectious Diseases/Food Allergy and Anaphylaxis Network (NIAID/FAAN) criteria.⁴² In the event of anaphylactic reaction or severe/serious hypersensitivity/allergic reaction, the patient must discontinue IP and emergency resuscitation measures implemented. In case of other mild to moderate hypersensitivity reaction, depending on the severity, the investigator may manage in accordance with the standard-of-care.

Anaphylaxis is highly likely when any one of the following 3 criteria is fulfilled:

1. Acute onset of an illness (minutes to several hours) with involvement of the skin, mucosal tissue, or both (eg, generalized hives, pruritus, or flushing, swollen lips-tongue-uvula) and at least 1 of the following:
 - a. Respiratory compromise (eg, dyspnea, wheeze-bronchospasm, stridor, reduced peak expiratory flow [PEF], hypoxemia)
 - b. Reduced blood pressure or associated symptoms of end-organ dysfunction (eg, hypotonia [collapse], syncope, incontinence)

2. Two or more of the following that occur rapidly after exposure to a likely allergen for that patient (minutes to several hours):
 - a. Involvement of the skin-mucosal tissue (eg, generalized hives, itch-flush, swollen lips-tongue-uvula)
 - b. Respiratory compromise (eg, dyspnea, wheeze-bronchospasm, stridor, reduced PEF, hypoxemia)
 - c. Reduced blood pressure or associated symptoms (eg, hypotonia [collapse], syncope, incontinence)
 - d. Persistent gastrointestinal symptoms (eg, crampy abdominal pain, vomiting)
3. Reduced blood pressure after exposure to known allergen for that patient (minutes to several hours):
 - a. Systolic blood pressure of less than 90 mm Hg or greater than 30% decrease from the patient's baseline

6.2.2.6.2 *Injection Site Reactions*

Injection site reactions are to be captured and reported as AEs. These will include Grades 2 to 5 injection site erythema, pain, and induration (see [APPENDIX 6](#)). The investigator should provide a clear description of the observed or reported AE including location and severity. All concomitant treatments used to treat injection site reactions should be recorded and captured in the eCRF, together with the AE of injection site reactions.

6.2.2.6.3 *Potential Drug-Induced Liver Injury*

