9.2 DMC

This study will use an external DMC. The DMC is an independent committee established to provide oversight of safety considerations in study and to provide advice to the sponsor regarding actions the committee deems necessary for the continuing protection of enrolled patients and those yet to be recruited to the trial as well as for the continuing validity and scientific merit of the study results. The DMC is charged with assessing such actions in light of an acceptable benefit/risk profile for BOS161721. The recommendations made by the DMC (ie, dose escalation, etc.) will be forwarded to the sponsor for final decision. The sponsor will forward such decisions, which may include summaries of safety data which are not endpoints, to regulatory authorities, as appropriate.

The sponsor will appoint a DMC for the periodic review of available study data. The DMC is an independent group of experts that advises the sponsor and the study investigators. The members of the DMC serve in an individual capacity and provide their expertise and recommendations. The primary responsibilities of the DMC are to (1) periodically review and evaluate the

accumulated study data for participant safety, study conduct, and progress, (2) make recommendations to the sponsor concerning the continuation, modification, or termination of the study and (3) suggest dose for POC portion of the study as described in [Section 3.1.1.3](#).

The DMC considers study-specific data as well as relevant background knowledge about the disease, test agent, or patient population under study. The DMC is responsible for defining its deliberative processes, including event triggers that would call for an unscheduled review, stopping guidelines, unmasking (unblinding), and voting procedures prior to initiating any data review. The DMC is also responsible for maintaining the confidentiality of its internal discussions and activities as well as the contents of reports provided to it.

The DMC will have access to unblinded treatment information during the clinical trial. Details regarding management and process of this committee are found in the DMC Charter.

The DMC may recommend termination of BOS161721 treatment arm or the entire BOS161721 MAD/POC trial for any safety concern that is felt to outweigh potential benefits. The recommendation must be supported by the sponsor as indicated in the DMC Charter.

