1.2.5.1 Anaphylaxis and Serious Allergic Reactions

As with the administration of any foreign protein and/or other biological agents, acute hypersensitivity reactions, including acute anaphylactic/hypersensitivity, severe allergic, and anaphylactoid reactions may follow infusion of mAbs and can be caused by various mechanisms. These acute hypersensitivity reactions may be severe and result in death.

Anaphylaxis will be defined according to the National Institute of Allergy and Infectious Diseases/Food Allergy and Anaphylaxis Network (NIAID/FAAN) criteria,³⁴ and are discussed in [Section 7.2.2.6.1](#).

Based on the limited Phase 1 SAD study (BOS161721-01), anaphylaxis and serious allergic reactions in subjects who received BOS161721 was not observed.

Patients with a known history of allergy or severe hypersensitivity reaction to any component of BOS161721 formulation or patients with a history of anaphylaxis to any other biological therapy such as mAbs will be excluded from studies with BOS161721. In addition, appropriate drugs and medical equipment to treat acute hypotensive, bronchoconstrictive, or anaphylactic reactions will be immediately available at the unit and study personnel will be trained to recognize and treat these reactions.

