1.2.5.4 Infections

BOS161721 is expected to diminish the activity of T-cell, B-cell and NK-cell lines. Like other medications modulating immune response, BOS161721 may increase the potential risk for infection, including serious infections. IL-21 produced by CD4⁺ Th cells is required to sustain the anti-viral function of CD8⁺ T-cells against chronic viral infections. Nonclinical evidence suggests that the risk of chronic viral infection recurrence or increased severity may occur with IL-21 inhibition.³⁵

These conditions will be fully characterized with clinical descriptions and routine laboratory and/or specialty testing and treated where indicated with appropriate local standard of care.

Patients with a history of opportunistic infection, including recurrent or severe disseminated herpes zoster or disseminated herpes simplex within the last 3 years, or any other underlying pathology predisposing to serious infection, are excluded from studies with BOS161721 (for further details please refer to the current IB for BOS161721).

Patients will be assessed for hepatitis B, and C, and HIV-1/2 combination, at screening.

Cryptosporidium Infection

Cryptosporidium infection was noted in patients with an IL-21 receptor loss-of-function gene mutation and similar findings of cryptosporidium infection have been observed in immunosuppressed liver transplant and human immunodeficiency virus patients.^{36,37} Since

BOS161721 is expected to diminish the immunosurveillance activity of T-cell, B-cell, and NK-cell lines, a similar risk is biologically plausible with prolonged exposure to BOS161721.

Since the risk of opportunistic cryptosporidium infection increases with low levels of CD4+ T-cells,³⁷ patients with a CD4+ count $< 500 \text{ cell/mm}^3$ were excluded from the Phase 1 SAD study (BOS161721-01), and will be excluded from the proposed MAD/POC studies. Patients exposed to investigational product who develop diarrhea during the course of the study should immediately undergo an assessment for opportunistic infection including stool for ova and parasites and stool examination for cryptosporidium. Positive cryptosporidium in stool sample at screening is an exclusion. Treatment by the investigator where indicated should be guided by findings and be consistent with local standard of care.

Based on the limited Phase 1 SAD study (BOS161721-01), infections in subjects who received BOS161721 was not observed.

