4.1.1.1 Dose Escalation for the MAD Study

The MAD study design is staggered, where after the 6 patients in Cohort 1 have received 2 doses and have completed 2 weeks of follow-up after the second dose, Cohort 2 begins dosing (after DMC evaluation of the safety and tolerability data from Cohort 1). Similarly, after 8 of the 12 patients in Cohort 2 have received 2 doses and have completed 2 weeks of follow-up after the second dose, Cohort 3 begins dosing after DMC evaluation of the safety and tolerability data from Cohorts 1 and 2. Each cohort will continue at their assigned dose level through their respective 6-month treatment periods (See Study Schematic, [Section 4.1](#)). If > 3 patients discontinue the study in a cohort, he/she may be replaced.

Criteria for dose escalation are further described in the DMC Charter. See [Section 4.1.1.2](#) for additional details about DLTs.

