4.1.1.2 Dose Limiting Toxicity (DLT)

Severity of adverse events will be graded according to National Cancer Institute Common Terminology Criteria for Adverse Events (NCI CTCAE) version 4.03. For the purpose of dose escalation, any of the following AEs occurring after study drug administration, which are attributable to the study drug, will be considered DLTs:

Hematologic:

- Grade 4 neutropenia
- Grade 3 neutropenic infection
- Grade 3 thrombocytopenia with bleeding
- Grade 4 thrombocytopenia

Non-Hematologic:

- Grade 3 or above toxicities, persisting after optimal treatment with standard medical therapy (eg, anti-emetics, anti-diarrheals)
- Drug-induced liver injury ([DILI], Hy's Law), as defined in [Section 7.2.2.6.3](#)

Investigators should always manage their patients according to their medical judgment which may include interruption of study drug based on the particular clinical circumstances.

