4.1.1.3 DMC Recommendations

During scheduled meetings, the DMC will review relevant study data for safety or benefit-risk concern. During the MAD study, the DMC may provide the following recommendations to the sponsor:

- Expanding a cohort at a specific dosing level, or repeating a lower dose in a subsequent cohort
- Continuing a dose level for a given cohort
- Escalating a dose level for a subsequent cohort
- Termination of current or previous cohort(s)

Further dosing in a given cohort will be halted if 2 or more DLTs are identified intra- and inter-patients dosed. For the POC study, the DMC and Boston Pharmaceuticals will conduct a data review for the IA1 to suggest which dose should be carried forward into the POC Phase 2

study. This POC dose decision will be based on evaluation of the PK, safety (inclusive of dose-limiting toxicity [DLT]), and tolerability data (and available PD/biomarker data) from Cohorts 1, 2, and 3; this dose will not exceed doses tested during the MAD study. The DMC will be reviewing all relevant data from Cohorts 1, 2, and 3 that is available at the time the last patient in Cohort 3 completes the Day 44 visit (2 weeks after dose 2). Details are provided in the DMC Charter.

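### As worded, a drug-related anaphylaxis or severe allergic reaction that resolves on treatment is not a DLT and does not count toward the two-DLT cohort halt

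*Protocol*

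**What the plan says.** Protocol V2.0 section 4.1.1.2 defines DLTs by a closed list, restricted to events attributable to study drug. The hematologic entries are Grade 4 neutropenia, Grade 3 neutropenic infection, Grade 3 thrombocytopenia with bleeding and Grade 4 thrombocytopenia. The non-hematologic entries are Hy's Law liver injury and "Grade 3 or above toxicities, persisting after optimal treatment with standard medical therapy (eg, anti-emetics, anti-diarrheals".

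Section 4.1.1.3 attaches a fixed consequence: "Further dosing in a given cohort will be halted if 2 or more DLTs are identified intra- and inter-patients dosed". The same section makes DLTs an input to the Phase 2 dose: "This POC dose decision will be based on evaluation of the PK, safety (inclusive of dose-limiting toxicity [DLT]), and tolerability data".

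On hypersensitivity, V2.0 section 1.2.5.1 warns: "These acute hypersensitivity reactions may be severe and result in death". It also reports that neither anaphylaxis nor serious allergic reactions were seen in the single-dose study. V3.0 section 6.2.2.6.1 says that after an anaphylactic or severe/serious allergic reaction "the patient must discontinue IP and emergency resuscitation measures implemented".

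Beyond the list, V2.0 section 4.1.1.1 says "Criteria for dose escalation are further described in the DMC Charter", and V3.0 section 9.2 says "The DMC is responsible for defining its deliberative processes, including event triggers that would call for an unscheduled review, stopping guidelines".

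**The concern.** The examples attached to the persistence condition, anti-emetics and anti-diarrheals, suggest that it was written for symptoms that supportive care can control. The wording is not limited in that way. It governs every Grade 3 or higher non-hematologic toxicity except Hy's Law liver injury.

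Acute hypersensitivity fits this condition badly. Such a reaction may be life-threatening and yet resolve quickly once treated, so prompt recovery says little about whether the dose is safe for the next patient. The protocol treats the event as serious enough to end that patient's dosing, but the rule that judges the dose for everyone else need not register it.

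Two things are at stake. Two such reactions in one cohort would not trigger the automatic halt. And the DLT tally that feeds the Phase 2 dose choice would omit them, although the DMC would still see them among the safety data.

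**Working it through.** The protocol states no operating characteristic for the DLT rule, so there is no figure to reproduce. The check is textual, followed by an illustration of size.

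**Step 1: tracing the event through the list.** Take a drug-attributable anaphylaxis or severe/serious allergic reaction that resolves on treatment.

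| Entry | Does the event match? |
|---|---|
| Four hematologic entries | No |
| Hy's Law liver injury | No |
| Grade 3+ non-hematologic, persisting after optimal treatment | No, because it resolved (if graded below 3, it also fails on grade) |

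Its contribution to the count is 0. Persistence has no time limit, so a slow, unresponsive or fatal reaction can still count.

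**Step 2: does the wording carry into V3.0?** V1.0 and V2.0 agree. The V2.0 change log records a deletion in this very section, so edits to it do get logged. The V3.0 log (Appendix 7) changes the neighbouring sections 3.1.1.1 and 3.1.1.3 and lists no DLT edit. That log covers significant changes only, so carry-over is a reasonable inference, not something seen.

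**Step 3: illustrative size if the events counted.**

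Inputs: 5 active patients in Cohort 1 and 9 in each of Cohorts 2 and 3 (V2.0 section 4.1.1), 23 in all. Assumptions: a true rate p of 2% or 5% per active patient over full dosing, independent patients, at most one event each, all attributable to drug.

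P(at least 2 affected) = 1 − (1−p)^n − n·p·(1−p)^(n−1)

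- n = 5, p = 0.02: 1 − 0.90392 − 0.09224 = 0.0038
- n = 5, p = 0.05: 1 − 0.77378 − 0.20363 = 0.0226
- n = 9, p = 0.02: 1 − 0.83375 − 0.15314 = 0.0131
- n = 9, p = 0.05: 1 − 0.63025 − 0.29854 = 0.0712

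At least one of the three cohorts halted = 1 − (1−P5)(1−P9)²:

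- p = 0.02: 1 − 0.99616 × 0.98689² = 0.030
- p = 0.05: 1 − 0.97741 × 0.92879² = 0.157

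At least one such event among 23 active patients = 1 − (1−p)^23: 0.37 at p = 0.02 and 0.69 at p = 0.05.

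Wider range: p = 0.01 gives P(at least 2) of 0.0010 (n = 5) and 0.0034 (n = 9); p = 0.10 gives 0.0815 and 0.2252.

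The halt rule also counts two DLTs in one patient, and one such reaction could combine with a DLT of another kind. For a given p, these per-patient figures are therefore lower bounds on the halts added.

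**The case against.** The strongest reply is that the DLT list is not the whole safety rule. Each escalation step needs DMC evaluation of safety and tolerability data. The DMC may recommend repeating a lower dose or terminating a cohort, and it sets its own triggers and stopping guidelines. The Charter adds escalation criteria. Anaphylaxis and serious allergic reactions are events of special interest, reported immediately or within 24 hours. All of this stands. A reader might infer that such reactions would go unreviewed or that nothing would stop dosing; the documents do not support that. But these routes are discretionary: under V3.0 section 9.2 the DMC's recommendations go to the sponsor for final decision, whereas the halt at 2 DLTs is fixed. What the Charter says is unknown.

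A second reply is that the text shown is superseded. That limits the point to an inference about V3.0, and the sponsor should check section 3.1.1.2 there.

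A third is that the added halt would seldom operate. The 2% to 5% rates have no source in the protocol and cover all seven doses. Cohort 1's escalation review falls two weeks after dose 2. With constant risk per dose, a 5% full-course rate is 1 − 0.95^(2/7), about 1.5%, by then, and the chance of two affected among five active patients is about 0.2%. This is fair, and it is why the benefit is mainly a complete count.

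A reader might extend the point to Grade 3+ non-neutropenic infection, since V2.0 section 1.2.5.4 says "BOS161721 may increase the potential risk for infection, including serious infections" and Grade 3 neutropenic infection counts without a persistence condition. That case is weaker. Patients take background immunosuppressants, antimalarials or prednisone. The causality definition requires that concurrent disease or other drugs cannot explain the event. And an infection still present during treatment can be read as persisting. A blanket rule for infection is a debatable trade-off, not a required correction.

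**Conclusion.** The point holds for anaphylaxis and severe/serious allergic reaction. As worded in V2.0, such an event that is drug-attributable and resolves on treatment adds 0 to the DLT count and so nothing to the mandatory halt, while the same protocol takes the patient off drug. This follows from the text and needs no assumed rate, but its application to V3.0 is inferred.

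The practical size is modest. None was observed in the single-dose study and no expected rate is given. At the assumed 2% to 5%, the chance that the DLT tally would miss at least one such event among 23 active patients is 37% to 69%, provided every event resolves on treatment. The chance that counting them would by itself halt a given cohort is 0.4% to 7.1%, depending on rate and cohort size. The correction therefore mainly completes the DLT count and adds a halt only when events cluster. It is worth making because these reactions can be fatal and the rewording is cheap. Confidence is medium, because neither the V3.0 section nor the Charter has been seen.

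**What to change.** In the DLT section, confine the persistence condition to manageable symptoms such as nausea, vomiting and diarrhea. Add drug-attributable anaphylaxis and drug-attributable severe/serious allergic reaction as DLTs in their own right, regardless of response to treatment. Align the Charter text.

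The cost is wording in one definition and the matching Charter passage; no new data are needed. The downside is a slightly higher chance of halting a cohort: illustratively 0.4% to 2.3% with 5 active patients, 1.3% to 7.1% with 9, and 3.0% to 15.7% for at least one halt across the three cohorts, at assumed rates of 2% to 5%.

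Whether drug-attributable Grade 3+ non-neutropenic infection should also count regardless of response is for the sponsor and DMC to decide, given the background immunosuppression.

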4.1.1.3 DMC Recommendations

During scheduled meetings, the DMC will review relevant study data for safety or benefit-risk concern. During the MAD study, the DMC may provide the following recommendations to the sponsor:

- Expanding a cohort at a specific dosing level, or repeating a lower dose in a subsequent cohort
- Continuing a dose level for a given cohort
- Escalating a dose level for a subsequent cohort
- Termination of current or previous cohort(s)

Further dosing in a given cohort will be halted if 2 or more DLTs are identified intra- and inter-patients dosed. For the POC study, the DMC and Boston Pharmaceuticals will conduct a data review for the IA1 to suggest which dose should be carried forward into the POC Phase 2

study. This POC dose decision will be based on evaluation of the PK, safety (inclusive of dose-limiting toxicity [DLT]), and tolerability data (and available PD/biomarker data) from Cohorts 1, 2, and 3; this dose will not exceed doses tested during the MAD study. The DMC will be reviewing all relevant data from Cohorts 1, 2, and 3 that is available at the time the last patient in Cohort 3 completes the Day 44 visit (2 weeks after dose 2). Details are provided in the DMC Charter.

4.1.2 POC Phase 2 Study

4.1.2.1 BOS161721 Dose

The optimal dose evaluation is chosen based on MAD Phase 1b safety, tolerability, immunogenicity, and PK and PD data. The dose will be communicated by a letter to site investigators participating in the POC Phase 2 study, and to the IRB/IEC.

4.1.2.2 POC Study Design

For the POC study, approximately 156 patients will be randomized to active or placebo groups in a 2:1 ratio.

As in the MAD study, each patient in the POC study may receive a total of 7 SC monthly doses of study drug on Days 0, 30, 60, 90, 120, 150, and 180. Assessments will be completed according to the Schedule of Assessments ([Section 4.3](#)). Dose selection will be based on the sponsor's assessment of safety, tolerability, immunogenicity, and PK and PD data from the MAD study of 30 patients treated with BOS161721/placebo.

[figure not shown]
Data from approximately 60 patients (including the 12 from the MAD study, or 6 fewer if the low dose is chosen who are in the cohort of the chosen dose for the POC study) who complete 3 months of treatment will be used in the IA2 at Day 90 to assess if the trial could stop for an early futility conclusion (see [Section 9.3](#) for details regarding the IA). If futility is not claimed in the IA2, the POC study will continue to approximately 156 patients.

Following the 6-month treatment period, primary and secondary efficacy endpoints will be assessed for each patient after providing their Day 180 disease activity assessments.

DMC monitoring will be conducted periodically throughout the study as described in the DMC charter.

4.2 Study Schematic

Figure 2. Study Diagram for MAD Phase 1b and POC Phase 2 Studies

A = active drug (BOS161721); P = placebo

4.3 Schedule of Assessments

Table 1. Schedule of Assessments - Phase 1b - Multiple Ascending Dose

	Screen ^a	Enroll	Treatment Period Follow-Up											Safety Follow-Up		
Days	-28 to -1	0	7 (± 1)	15 (± 3)	30 (± 3)	44 (± 3)	60 (± 3)	90 (± 3)	120 (± 3)	150 (± 3)	180 (± 3)	187 (± 3)	195 (± 3)	210 (± 3)	240 (± 3)	270 (± 3)
Visit Number	1	2	--	3	4	5	6	7	8	9	10	--	--	11	12	13
GENERAL ASSESSMENTS																
Informed consent	X															
Inclusion/Exclusion criteria	X															
Medical history	X															
Demographics	X															
SLICC Criteria for SLE	X															
Concomitant medication ^b	X	X	X	X	X	X	X	X	X	X	X	X	X	X	X	X
Randomization ^c		X														
BOS161721 or placebo dosing		X			X		X	X	X	X	X					
SAFETY ASSESSMENTS																
Full physical exam	X	X														
Chest x-ray ^d	X															
C-SSRS	X	X						X			X					
AEs and SAEs		X	X	X	X	X	X	X	X	X	X	X	X	X	X	X
12-lead ECG ^e	X	X			X			X								X
Injection site reaction assessment ^f		X	X		X		X	X	X	X	X	X	X	X	X	X
Targeted physical examination				X	X	X	X	X	X	X	X			X	X	X
Vital signs (BP, HR, and temperature) ^g	X	X		X	X	X	X	X	X	X	X			X	X	X
EFFICACY ASSESSMENTS																
BILAG-2004 Index	X	X			X		X	X	X	X	X			X	X	X

Table 1. Schedule of Assessments - Phase 1b - Multiple Ascending Dose

	Screen ^a	Enroll	Treatment Period Follow-Up											Safety Follow-Up		
Days	-28 to -1	0	7 (± 1)	15 (± 3)	30 (± 3)	44 (± 3)	60 (± 3)	90 (± 3)	120 (± 3)	150 (± 3)	180 (± 3)	187 (± 3)	195 (± 3)	210 (± 3)	240 (± 3)	270 (± 3)
Visit Number	1	2	--	3	4	5	6	7	8	9	10	--	--	11	12	13
SLEDAI-2K	X	X			X		X	X	X	X	X			X	X	X
PGA of disease activity	X	X			X		X	X	X	X	X			X	X	X
ACR-28 joint count	X	X			X		X	X	X	X	X			X	X	X
CLASI	X	X			X		X	X	X	X	X			X	X	X
CCI		X			X		X	X	X	X	X			X	X	X
SLICC/ACR Damage Index		X									X					
CCI		X			X		X	X	X	X	X			X	X	X
LABORATORY ASSESSMENTS																
CD4+ count	X	X		X	X	X		X			X					
Clinical laboratory assessments (hematology and clinical chemistry) ^h	X	X			X	X	X	X	X	X	X			X	X	X
Coomb's test direct ⁱ	X	X			X		X	X	X	X	X			X	X	X
Total IgG and IgM	X	X		X	X	X		X			X					
Plasma CCI	X	X			X		X	X	X	X	X			X	X	X
Plasma CCI & CCI	X	X		X	X		X	X			X					
Whole blood for leukocyte immunophenotype	X	X		X	X		X	X			X					
ADA ^j		X		X	X		X	X			X					X
nAb ^k								X			X					
pSTAT3		X			X	X	X	X			X					X
CCI		X									X					
Whole blood RNA collection		X		X	X			X								X

Table 1. Schedule of Assessments - Phase 1b - Multiple Ascending Dose

	Screen ^a	Enroll	Treatment Period Follow-Up											Safety Follow-Up		
Days	-28 to -1	0	7 (± 1)	15 (± 3)	30 (± 3)	44 (± 3)	60 (± 3)	90 (± 3)	120 (± 3)	150 (± 3)	180 (± 3)	187 (± 3)	195 (± 3)	210 (± 3)	240 (± 3)	270 (± 3)
Visit Number	1	2	--	3	4	5	6	7	8	9	10	--	--	11	12	13
CCI																
	X	X			X		X	X	X	X	X			X ^l	X ^l	X ^l
CRP	X							X								X
Serum pregnancy test (women)	X															
FSH (postmenopausal women)	X															
Urine pregnancy test (women) ^m		X			X		X	X	X	X	X					
TB test (QuantiFERON-TB Gold In-Tube) ^d	X															
Serology (hepatitis B and C, HIV-1/2 combination)	X															
Stool sample ⁿ	X															
Spot urine for protein/creatinine ratio	X	X			X		X	X	X	X	X			X	X	X
Urinalysis	X	X			X		X	X	X	X	X			X	X	X
PK Labs																
Predose ^o		X			X		X	X	X	X	X					
Postdose		X ^p	X	X	X ^p						X ^p	X	X	X	X	X

Table 1. Schedule of Assessments - Phase 1b - Multiple Ascending Dose

	Screen ^a	Enroll	Treatment Period Follow-Up											Safety Follow-Up		
Days	-28 to -1	0	7 (± 1)	15 (± 3)	30 (± 3)	44 (± 3)	60 (± 3)	90 (± 3)	120 (± 3)	150 (± 3)	180 (± 3)	187 (± 3)	195 (± 3)	210 (± 3)	240 (± 3)	270 (± 3)
Visit Number	1	2	--	3	4	5	6	7	8	9	10	--	--	11	12	13

Abbreviations: ACR = American College of Rheumatology; ADA= anti-drug antibody; AE = adverse event; CCI [REDACTED]; BILAG = British Isles Lupus Assessment Group; BP = blood pressure; C = complement; CD4+ = cluster of differentiation 4; CLASI = Cutaneous Lupus Area and Severity Index; CRP = C-reactive protein; C-SSRS = Columbia Suicide Severity Rating Scale; ECG = electrocardiogram; CCI [REDACTED]; FSH = follicle stimulating hormone; HR = heart rate; HIV = human immunodeficiency virus; IgG = immunoglobulin G; IgM = immunoglobulin M; IL-21 = interleukin 21; IV = intravenous; nAb = neutralizing antibody; PGA = Physician’s Global Assessment; PK = pharmacokinetic; pSTAT3 = phosphorylated signal transducer and activator of transcription 3; RNA = ribonucleic acid; RNP = ribonucleoprotein; SAE = serious adverse event; SC = subcutaneous; CCI [REDACTED]; SLEDAI-2K = SLE Disease Activity Index 2000; SLICC = Systemic Lupus International Collaborating Clinics; CCI [REDACTED]; TB = tuberculosis; TDAR = T-cell dependent antigen response.

- ^a Screening assessments will be performed over more than 1 visit.
- ^b Concomitant use of oral corticosteroids: A maximum daily dose of 30 mg/day of oral CS will be acceptable for eligibility for the study, however, the daily dose must be tapered down to a maximum of 10 mg/day for at least 5 days prior to Day 0 (randomization day). See [Section 5.6.1](#) for further details.
- ^c Randomization should occur after patient eligibility has been confirmed by central eligibility review.
- ^d If patients have had a TB test and chest x ray within 3 months prior to screening, then these assessments do not need to be repeated during screening. The results of TB screening, which includes the QuantiFERON[®]-TB Gold In-Tube (QFT-G) test and a chest x-ray, conducted in the 3 months prior to screening or during the screening period must be documented in study records prior to randomization (Day 0).
- ^e ECGs will be performed after the patient has been supine for at least 5 minutes. On days of PK blood draws, the ECG will be collected before scheduled PK blood draws.
- ^f Injection site reaction assessments to be performed predose and at 2 hours postdose.
- ^g Vital signs will be assessed after the patient has been supine and at rest ≥ 5 minutes. Vital signs will be assessed on Day 0 at predose and at 1 and 2 hours postdose, as well as on each of the scheduled outpatient days in the table above (excluding PK-only site visits at Days 7, 187, and 195). When the timing of these measurements coincides with a blood collection, vital signs should be obtained prior to the time of the blood collection.
- ^h Clinical laboratory assessments will include a fasting glucose and lipid panel, with exception of screening (Visit 1) which will be nonfasting.
- ⁱ When clinically indicated.
- ^j Blood samples for ADA analysis will be collected up to Day 90 from all patients. Subsequent ADA samples will be collected from all patients but only assayed if the patient had a positive ADA on Day 90.
- ^k nAb is assessed if patient is positive for ADA.
- ^l Only dsDNA collected during safety follow-up visits.
- ^m Urine pregnancy test will be collected on WOCBP prior to study drug administration on dosing visits.
- ⁿ Cryptosporidium test is required at screening. If a patient develops diarrhea during the study a stool sample must be provided to test for ova, parasites, and cryptosporidium.
- ^o Predose samples occur on study drug administration visit days.
- ^p Postdose samples will be collected at 4, 8, and 24 hours after study drug administration on Days 0, 30, and 180.

Table 2. Schedule of Assessments - Phase 2 Proof of Concept (POC) Study

	Screen ^a	Enroll	Treatment Period Follow-up									Safety Follow-Up		
Days	-28 to -1	0	15 (± 3)	30 (± 3)	60 (± 3)	90 (± 3)	120 (± 3)	150 (± 3)	180 (± 3)	187 (± 3)	195 (± 3)	210 (± 3)	240 (± 3)	270 (± 3)
Visit Number	1	2	3	4	5	6	7	8	9	--	--	10	11	12
GENERAL ASSESSMENTS														
Informed consent	X													
Inclusion/Exclusion criteria	X													
Medical history	X													
Demographics	X													
SLICC Criteria for SLE	X													
Concomitant medication ^b	X	X	X	X	X	X	X	X	X	X	X	X	X	X
Randomization ^c		X												
BOS161721 or placebo dosing		X		X	X	X	X	X	X					
SAFETY ASSESSMENTS														
Full physical exam	X	X												
Chest x-ray ^d	X													
C-SSRS	X	X				X			X					
AEs and SAEs		X	X	X	X	X	X	X	X	X	X	X	X	X
12-lead ECG ^e	X	X		X		X								X
Injection site reaction assessment ^f		X		X	X	X	X	X	X	X	X	X	X	X
Targeted physical examination			X	X	X	X	X	X	X			X	X	X
Vital signs (BP, HR, and temperature) ^g	X	X	X	X	X	X	X	X	X			X	X	X
EFFICACY ASSESSMENTS														
BILAG-2004 Index	X	X		X	X	X	X	X	X			X	X	X
SLEDAI-2K	X	X		X	X	X	X	X	X			X	X	X
PGA	X	X		X	X	X	X	X	X			X	X	X
ACR-28 joint count	X	X		X	X	X	X	X	X			X	X	X
CLASI	X	X		X	X	X	X	X	X			X	X	X
CCI		X		X	X	X	X	X	X			X	X	X

Table 2. Schedule of Assessments - Phase 2 Proof of Concept (POC) Study

Days	Screen ^a	Enroll	Treatment Period Follow-up									Safety Follow-Up		
	-28 to -1	0	15 (± 3)	30 (± 3)	60 (± 3)	90 (± 3)	120 (± 3)	150 (± 3)	180 (± 3)	187 (± 3)	195 (± 3)	210 (± 3)	240 (± 3)	270 (± 3)
Visit Number	1	2	3	4	5	6	7	8	9	--	--	10	11	12
SLICC/ACR Damage Index		X							X					
CCI		X		X	X	X	X	X	X			X	X	X
LABORATORY ASSESSMENTS														
CD4+ count	X	X	X	X		X			X					
Clinical laboratory assessments (hematology and clinical chemistry) ^h	X	X		X	X	X	X	X	X			X	X	X
Coomb's test direct ⁱ	X	X		X	X	X	X	X	X			X	X	X
Total IgG and IgM	X	X	X	X		X			X					
Plasma CCI	X	X		X	X	X	X	X	X			X	X	X
Plasma CCI & CCI	X	X	X	X	X	X			X					
Whole blood for leukocyte immunophenotype	X	X	X	X	X	X			X					
ADA ^j		X	X	X	X	X			X					X
nAb ^k						X			X					
pSTAT3 ^l		X		X	X	X			X					
CCI		X							X					
Whole blood RNA collection		X	X	X		X								X
CCI	X	X		X	X	X	X	X	X			X ^m	X ^m	X ^m
CRP	X					X								X
Serum pregnancy test (women)	X													
FSH (postmenopausal women)	X													
Urine pregnancy test (women) ⁿ		X		X	X	X	X	X	X					
TB test (QuantiFERON-TB Gold In-Tube) ^d	X													
Serology (hepatitis B and C, HIV-1/2 combination)	X													

Table 2. Schedule of Assessments - Phase 2 Proof of Concept (POC) Study

	Screen ^a	Enroll	Treatment Period Follow-up									Safety Follow-Up		
Days	-28 to -1	0	15 (± 3)	30 (± 3)	60 (± 3)	90 (± 3)	120 (± 3)	150 (± 3)	180 (± 3)	187 (± 3)	195 (± 3)	210 (± 3)	240 (± 3)	270 (± 3)
Visit Number	1	2	3	4	5	6	7	8	9	--	--	10	11	12
Stool sample ^o	X													
Spot urine for protein/creatinine ratio	X	X		X	X	X	X	X	X			X	X	X
Urinalysis	X	X		X	X	X	X	X	X			X	X	X
PK Labs^p														
Predose ^q		X		X	X	X	X	X	X					
Postdose			X							X	X	X	X	X

Abbreviations: ACR = American College of Rheumatology; ADA= anti-drug antibody; AE = adverse event; **CCI**; BILAG = British Isles Lupus Assessment Group; BP = blood pressure; C = complement; CD4+ = cluster of differentiation 4; CLASI = Cutaneous Lupus Area and Severity Index; CRP = C-reactive protein; C-SSRS = Columbia Suicide Severity Rating Scale; ECG = electrocardiogram; **CCI**; **CCI**; FSH = follicle stimulating hormone; HR = heart rate; HIV = human immunodeficiency virus; IgG = immunoglobulin G; IgM = immunoglobulin M; IL-21 = interleukin 21; IV = intravenous; nAb = neutralizing antibody; PGA = Physician’s Global Assessment; PK = pharmacokinetic; pSTAT3 = phosphorylated signal transducer and activator of transcription 3; RNA = ribonucleic acid; RNP = ribonucleoprotein; SAE = serious adverse event; SC = subcutaneous; **CCI**; SLEDAI-2K = SLE Disease Activity Index 2000; SLICC = Systemic Lupus International Collaborating Clinics; **CCI**; TB = tuberculosis; TDAR = T-cell dependent antigen response.

- ^a Screening assessments will be performed over more than 1 visit.
- ^b Concomitant use of oral corticosteroids: A maximum daily dose of 30 mg/day of oral CS will be acceptable for eligibility for the study, however, the daily dose must be tapered down to a maximum of 10 mg/day for at least 5 days prior to Day 0 (randomization day). See Section 5.6.1 for further details.
- ^c Randomization should occur after patient eligibility has been confirmed. The actual randomization procedure can be completed on Day -1 after eligibility confirmation or the morning of Day 0 prior to dosing for logistical purposes.
- ^d If patients have had a TB test and chest x ray within 3 months prior to screening, then these assessments do not need to be repeated during screening. The results of TB screening, which includes the QuantiFERON[®]-TB Gold In-Tube (QFT-G) test and a chest x-ray, conducted in the 3 months prior to screening or during the screening period must be documented in study records prior to randomization (Day 0).
- ^e ECGs will be performed after the patient has been supine for at least 5 minutes. On days of PK blood draws, the ECG will be collected before scheduled PK blood draws.
- ^f Injection site reaction assessments to be performed predose and at 2 hours postdose.
- ^g Vital signs will be assessed after the patient has been supine and at rest ≥ 5 minutes. Vital signs will be assessed on Day 0 at predose and at 1 and 2 hours postdose, as well as on each of the scheduled outpatient days in the table above (excluding PK-only site visits at Days 187 and 195). When the timing of these measurements coincides with a blood collection, vital signs should be obtained prior to the time of the blood collection.
- ^h Clinical laboratory assessments will include a fasting glucose and lipid panel, with exception of screening (Visit 1) which will be nonfasting.

Table 2. Schedule of Assessments - Phase 2 Proof of Concept (POC) Study

	Screen ^a	Enroll	Treatment Period Follow-up									Safety Follow-Up		
Days	-28 to -1	0	15 (± 3)	30 (± 3)	60 (± 3)	90 (± 3)	120 (± 3)	150 (± 3)	180 (± 3)	187 (± 3)	195 (± 3)	210 (± 3)	240 (± 3)	270 (± 3)
Visit Number	1	2	3	4	5	6	7	8	9	--	--	10	11	12

ⁱ When clinically indicated.

^j Blood samples for ADA analysis will be collected up to Day 90 from all patients. Subsequent ADA samples will be collected from all patients but only assayed if the patient had a positive ADA on Day 90.

^k nAb is assessed if patient is positive for ADA.

^l Predose (trough) samples only.

^m Only **CCI** collected during safety follow-up visits.

ⁿ Urine pregnancy test will be collected on WOCBP prior to study drug administration on dosing visits.

^o Cryptosporidium test is required at screening. If a patient develops diarrhea during the study a stool sample must be provided to test for ova, parasites, and cryptosporidium.

^p PK samples will only be collected at the investigational sites that will be participating in the PK portion of the study.

^q Predose samples occur on study drug administration visit days.

